**Table 2: Analysis Visit Windows**

Visit Name	Visit Number	Target Start Day	Lower Limit	Upper Limit
Screening	1		-35	-14
Baseline Pre-dose	2		-14	-3
Day 1	3	1	1	1
Day 7	4	7	6	8
Day 14	5	14	13	15
Day 21	6	21	20	22

#### 6.1.7. Pooling of Sites

Not applicable.

#### 6.1.8. Derived Variables

- **TETRAS-PS Total score** = sum of the 16 individual item scores (only the maximum of the item 5 lower limb tremor scores will be counted), with a maximum total score of 64. There will be no missing value imputation performed.
- **TETRAS-PS Upper Limb Subscale score** = sum of the item 4, item 6, item 7 and item 8 scores (forward outstretched postural tremor, lateral “wing beating” postural tremor, kinetic tremor, Archimedes spirals, and dot approximation task from both sides of the body, as well as handwriting), with a maximum total score of 44. There will be no missing value imputation performed.
- **TETRAS-PS Upper Limb Tremor (Item 4) Total score** = sum of the 6 individual scores under item 4 scores (forward outstretched postural tremor, lateral “wing beating”

postural tremor, and kinetic tremor scores for left and right hand, respectively) from both sides of the body, with a maximum total score of 24. There will be no missing value imputation performed.

Commercially Confidential Information

- **Kinesia Upper Limb Tremor score** = sum of the scores from the extended arms posture, wing-beating posture, and kinetic “finger-to-chin” wearable sensor maneuvers from both sides of the body, with a maximum total score of 24. There will be no missing value imputation performed.
- **Change from baseline** = value at current time point – value at baseline.
  - For calculation of change from baseline to Day 14 for discontinued subjects their assessment value at the early termination (ET) visit should be used
- **Percent change from baseline** = (change from baseline / baseline) \* 100. If both baseline and change from baseline are 0 then percent change from baseline will be set to 0.
- **Study day** = number of days relative to the first dose date of study drug and will be calculated using the following formulas:  
For pre-dose: study day= Start Date/ Stop Date – first dose date;  
For post-dose: study day= Start Date/ Stop Date – first dose date + 1.
- **TEAE (treatment-emergent AE)** = any AE with an onset date/time after the first dose of treatment. If an AE was present at baseline and worsened on or after the first dose of treatment it will be considered a TEAE.
- **Orthostatic hypotension** is defined as a reduction in SBP of 20 mmHg or more, and/or a reduction in DBP of 10 mmHg or more, for the standing measurement compared to the supine or semi-supine measurement.
- **Time since first ET symptom** = Day 1 (Visit 3) date - Date of first ET symptom as recorded on the Disease History case report form (CRF) + 1
- **Time since ET diagnosis** = Day 1 (Visit 3) date - Date of ET diagnosis as recorded on the Disease History case report form (CRF) + 1
- **Study drug compliance** (capsule count) = total number of capsules taken / total number of expected doses from the first dose date to the last dose date, inclusive \* 100%.

- **Number of expected doses** for subjects who completed study treatment = number of capsules taken at the clinic + number of capsules dispensed for self-administration at home = [Day 14 (Visit 5) date – Day 1 (Visit 3) date + 1] x 6 capsules/day

Expected doses are summed up to the point of discontinuation (eg, if a subject discontinued, only planned doses up to that discontinuation day are counted in the denominator).

- **Number of capsules taken** = number of expected doses - number of capsules lost - number of unused capsules returned at next clinic visit, as collected in the case report form (CRF).

For subjects who discontinued and did not return remaining capsules, the number of capsules taken will include all doses up to the last dose the subject reported, or the discontinuation date (the second dose on that day will be excluded in this calculation).

For treatment completers with additional treatment (for example the subject received study treatments for 15 days) their number of expected doses remains 84. Thus, the resulting compliance rate will likely be over 100%.

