### **6.2 Early Termination Visit and Withdrawal Procedures**

The end of treatment for subjects completing the study is Follow-up Visit on Day 21 ( $\pm 1$  day). For subjects who are withdrawn from the study prior to completion, all Day 14 procedures will be performed at an Early Termination visit as indicated in the SOA ([Appendix A, Table 2](#)) and they will also complete the C-SSRS. Subjects withdrawing from the study early will not receive study drug on-site at the Early Termination visit.

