 The subject should be instructed to self-administer their first daily dose of CAD-1883 4 to 5 hours prior to the scheduled and/or anticipated dosing of the second daily dose of CAD-1883. The second daily dose of CAD-1883 should be taken in the clinic 4 to 5 hours after the first daily dose.

Commercially Confidential Information

 TETRAS Performance Subscale assessments at Screening, Baseline/Pre-dose, Days 1, 7, 14, and 21 will be recorded via videography for central rating.

 Screening: Commercially Confidential Information

 Performed between 2-4 hours following the second dose in the clinic.

 Performed between 2-4 hours following the second daily dose in the clinic.

 Wearable sensor measurement of upper-limb tremor will be captured once at the site, at any time during Screening and Day 21.

 Wearable sensor measurements of upper limb tremor will be captured at two different times during the Baseline/Pre-dose visit.

 Wearable sensor measurements of upper limb tremor will be captured once, 2 to 4 hours following the in-clinic dose. For Day 1, this is to be done 2-4 hours after the 2nd in-clinic dose.

 At the Baseline/Pre-dose visit, the “baseline” version of the C-SSRS will be administered. This version assesses Suicidal Ideation and Suicidal Behavior during the subject’s lifetime and during a predefined period. At the Day 21 visit (and the Early Termination visit for subjects withdrawing early), the “since last visit” version will be administered. The C-SSRS does not need to be completed at the Day 14 visit if it is not an Early Termination visit. During Early Termination visit, the subject will not receive study drug, will undergo all required procedures as well as the C-SSRS.

 (Protocol Amendment 3) Both doses of study drug are to be administered in the clinic with the second dose being administered 4-5 hours after the first.

 All laboratory collections on Days 1, 7, 14 should be performed after the TETRAS-PS assessment.

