## 5. Analysis Populations

The following analysis populations are planned for this study:

- **Safety Population:** The Safety population includes all subjects who took at least 1 dose of study drug, regardless of the Protocol Amendment under which subjects were enrolled. This population will be used to summarize all safety data.

- **Full Analysis Set (FAS):** The FAS consists of subjects in the Safety Population at least one TETRAS-PS assessment Total Score at Day 7, Day 14 or early termination visit. The FAS will be used to summarize all efficacy data.

Commercially Confidential Information

- **Per-Protocol Population:** The Per-Protocol Population includes all subjects in the FAS who did not have any major protocol deviation and follow the study protocol for TETRAS-PS assessment at Day 14 or ET visit.

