## Figure 2: Planned Table Shells

Table 14.1.1  
Subject Disposition  
All Enrolled Subjects

Category	Cohort-1 (N=XX)	Cohort-2 (N=XX)	Overall (N=XX)
Enrolled	XX	XX	XX
Analysis Populations:			
Safety Population [1]	XX (XX.X%)	XX (XX.X%)	XX (XX.X%)
FAS Population [2]	XX (XX.X%)	XX (XX.X%)	XX (XX.X%)
Commercially Confidential Information	XX (XX.X%)	XX (XX.X%)	XX (XX.X%)
Per-Protocol Population [4]	XX (XX.X%)	XX (XX.X%)	XX (XX.X%)
Completed Study	XX (XX.X%)	XX (XX.X%)	XX (XX.X%)
Prematurely Discontinued from Study	XX (XX.X%)	XX (XX.X%)	XX (XX.X%)
Reason for Discontinuation:			
Adverse Event	XX (XX.X%)	XX (XX.X%)	XX (XX.X%)
Death	XX (XX.X%)	XX (XX.X%)	XX (XX.X%)
Lack of Efficacy	XX (XX.X%)	XX (XX.X%)	XX (XX.X%)
Lost to Follow-Up	XX (XX.X%)	XX (XX.X%)	XX (XX.X%)
Newly Emerged Exclusion Criteria During Study	XX (XX.X%)	XX (XX.X%)	XX (XX.X%)
Non-Compliance with Study Drug	XX (XX.X%)	XX (XX.X%)	XX (XX.X%)
Physician Decision	XX (XX.X%)	XX (XX.X%)	XX (XX.X%)
Pregnancy	XX (XX.X%)	XX (XX.X%)	XX (XX.X%)
Protocol Violation	XX (XX.X%)	XX (XX.X%)	XX (XX.X%)
Study Terminated by Sponsor	XX (XX.X%)	XX (XX.X%)	XX (XX.X%)
Withdrawal by Subject	XX (XX.X%)	XX (XX.X%)	XX (XX.X%)
Other	XX (XX.X%)	XX (XX.X%)	XX (XX.X%)

Abbreviations: ADL = activities of daily living; FAS = full analysis set; ICF = informed consent form; CCI ; PS = performance subscale; TETRAS = Tremor Research Group Essential Tremor Rating Assessment Scale.

Note: Cohort-1 is composed of subjects enrolled under the Protocol Amendment 1. Protocol Amendment 1 was finalized on 03 Dec 2018 with dosing interval of 8±2 hours during entire treatment period (Day 1-14). Cohort-2 is composed of subjects enrolled under Amendment 2 or 3. Amendment 2 was finalized on 09 May 2019 and Amendment 3 on 09 July 2019. Dosing interval was changed to 4-5 hours on Days 1, 7 and 14 in both Amendments 2 and 3.

Percentages are n/Number of subjects in the enrolled\*100.

[1] The Safety population includes all subjects who took at least 1 dose of study drug.

[2] The FAS consists of subjects in the Safety Population at least one TETRAS-PS assessment Total Score at Day 7, Day 14 or early termination visit. The FAS will be used to summarize all efficacy data.

[3] Commercially Confidential Information

[4] The Per-Protocol Population includes all subjects in the FAS who did not have any major protocol deviation and follow the study protocol for TETRAS-PS assessment.  
Personal Protected Data

Source: Listing 16.2.1.1

Table 14.1.2.1  

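### SAP 6.1.8 enters early-termination scores as Day 14 without giving an observed Day 14 score precedence, and the SAP Table 2 Baseline window contradicts the schedule it claims to follow

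*SAP*

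**What the plan says.** **Day 14 value for discontinued subjects.** Under the change-from-baseline definition in SAP 6.1.8: "For calculation of change from baseline to Day 14 for discontinued subjects their assessment value at the early termination (ET) visit should be used". No study-day limit, dosing condition or order of preference is attached.

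**What a Day 14 score is.** For TETRAS-PS on Days 7 and 14, footnote 21 to the SAP schedule reads "Performed between 2-4 hours following the second daily dose in the clinic".

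**What an early-termination score is.** Protocol 6.2: "For subjects who are withdrawn from the study prior to completion, all Day 14 procedures will be performed at an Early Termination visit", and "Subjects withdrawing from the study early will not receive study drug on-site at the Early Termination visit". Footnote 25 to the SAP schedule repeats that no drug is given. The same protocol section says "The end of treatment for subjects completing the study is Follow-up Visit on Day 21", so a subject who leaves between Day 14 and Day 21 has not completed.

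**Populations.** SAP 5 admits to the Full Analysis Set (FAS) anyone in the Safety Population with "at least one TETRAS-PS assessment Total Score at Day 7, Day 14 or early termination visit". It thus names early termination as a visit distinct from Day 14.

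**Visit windows.** SAP 6.1.6 says the windows in Table 2 follow the schedule in Table 1. They apply only to unscheduled or repeated measurements, and only when the scheduled one is unavailable. Table 2 gives Screening -35 to -14, Baseline -14 to -3 and Day 7 as 6 to 8. It has no early-termination row. SAP Table 1 places the Baseline visit at most 3 days before Day 1, Protocol 6.1.3 allows 3 business days, and SAP 3.1 allows Day 7 only a one-day early margin.

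**The concern.** The secondary endpoints are changes from Baseline to Day 14 of twice-daily dosing, with the score taken at a fixed time after a dose. A score from an early withdrawal may follow only a few days of drug, or come after drug was stopped. SAP 6.1.8 puts both kinds of score into one mean and one test. Results are also planned by cohort, where each subject carries more weight than in the overall group.

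The missing order of preference is a separate gap. A subject who attends Day 14 and withdraws before Day 21 has finished the 14-day treatment period. Protocol 6.2 then calls for an early-termination visit, and SAP 6.1.8 as worded would take that later off-drug score in place of a valid Day 14 one.

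The Table 2 error is of another kind: the table disagrees with its stated source. If a scheduled baseline is missing, a repeat on Day -2 or -1 falls outside the window, while a value from the washout period falls inside it.

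**Working it through.** **1. Can the two scores be equivalent by construction?**
- Day 14: Days 13 to 15, 2 to 4 hours after a supervised second daily dose.
- Early termination: any day before completion, with no on-site dose. A dose taken at home that day is not ruled out, so time since last dose is unspecified rather than known to be long.

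The procedures match. The dosing condition and study day do not.

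**2. Effect of including early-termination scores.** The plan states no power, dropout, effect or SD figure, so there is none to reproduce. Only n = 30 (the enrolment ceiling) and the two-sided 0.05 level come from the documents. Everything else here is assumed: mean Day 14 change -6, SD 8, k early-termination scores, and a difference D between the mean early-termination change and the mean Day 14 change. I take D = +6 (no change at early termination) and D = -3 (a change 3 points larger).

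- Shift in the mean = (k/n) × D.
- Mixture mean = -6 + (k/n)D.
- Mixture variance = 64 + (k/n)(1 - k/n)D².
- Power is from the noncentral t for the paired t-test, which SAP 8.2 uses unless normality is rejected.
- The comparator is the same trial with these scores left out: n - k subjects, mean -6, SD 8.

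| k | D | Shift in mean | Mixture mean, variance | Power, included | Power, omitted |
|---|---|---|---|---|---|
| 3 | +6 | 3/30 × 6 = +0.6 | -5.4, 67.24 | 93.6% | 96.3% (n = 27) |
| 6 | +6 | 6/30 × 6 = +1.2 | -4.8, 69.76 | 86.0% | 94.0% (n = 24) |
| 3 | -3 | 3/30 × (-3) = -0.3 | -6.3, 64.81 | 98.5% | 96.3% |
| 6 | -3 | 6/30 × (-3) = -0.6 | -6.6, 65.44 | 99.1% | 94.0% |

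The shifts are in points on a 64-point scale.

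**3. Table 2 against Table 1**, using the pre-dose study-day formula in SAP 6.1.8 (date minus first-dose date):
- Table 2 Baseline, -14 to -3: 12 days.
- At most 3 days before Day 1: Days -3 to -1. Shared: Day -3. Excluded although allowed: Days -2 and -1. Admitted although outside: 12 - 1 = 11 days.
- 3 business days: 3 calendar days from a Monday or Tuesday baseline, 5 from Wednesday to Friday, so at widest Days -5 to -1. Shared: Days -5, -4 and -3. Excluded: Days -2 and -1. Outside: 12 - 3 = 9 days.
- Day -14 lies in both the Screening and Baseline rows.
- Day 7: the schedule gives Days 6 to 7 and Table 2 gives 6 to 8, one day extra.
- Screening, Day 1, Day 14 and Day 21 agree with the schedule.

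**The case against.** **The rule is deliberate.** The schedule has one combined Day 14/Early Termination column, and Protocol 4.4 equates the two visits. Using the score keeps discontinuers in the analysis. This stands, and is why the rule should be kept. The shared column fixes which procedures are done; it does not make the scores equivalent.

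**Replacement of a valid Day 14 score is unlikely.** The Visit Status listing (16.2.1.2) asks about early termination only where the scheduled visit was not completed, which suggests the visit is meant as an alternative to a missed one. This largely stands as to intent. But a listing layout does not decide which value enters an analysis, and neither SAP 6.1.8 nor Protocol 6.2 contains the restriction.

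**Redaction.** Parts of SAP 5, 8.2.1 to 8.2.3 and 10, and the visible bodies of 6.1.4 and 11, are blacked out. A sensitivity analysis may sit there, so its absence cannot be asserted.

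**The count is not hidden.** Table 14.1.1 reports premature discontinuations by cohort and overall, which caps the number of early-termination scores. The listings carry termination date, last-dose time and minutes after dosing. This stands. The visible efficacy shells still have no separate row for these scores.

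**Stakes are modest.** The primary endpoint is safety and no power analysis was done. This stands.

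**Per-Protocol.** A reader might infer that this population is misdefined because it accepts subjects who "follow the study protocol for TETRAS-PS assessment at Day 14 or ET visit". The documents do not support that: an early-termination assessment without on-site drug is what the protocol prescribes.

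**Conclusion.** Both points hold within limits.

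SAP 6.1.8 lets early-termination scores, unrestricted by study day or time since last dose, count as Day 14, and does not say that an observed Day 14 score comes first. The first is an analytic weakness in a legitimate prespecified rule. The second is a gap in wording that the listing suggests was unintended.

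Size and direction of bias cannot be determined. Under the stated assumptions, inclusion costs 2.7 percentage points of power at k = 3 (96.3 - 93.6) and 8.0 at k = 6 (94.0 - 86.0) if early-termination subjects show no change. It adds power if their change is 3 points larger. A reader might infer a larger loss by comparing with a trial without dropout (98%), but that charges the cost of dropout itself to the rule. Nor do the documents support reading every early-termination score as off drug, or the bias as always toward no effect.

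Table 2 is wrong as written for Baseline and Day 7. A reader might infer that scheduled baselines are rejected. They are not: scheduled visits are analysed as scheduled, the windows act only on stand-in values, and SAP 6.1.1 narrows the reach further by tying baseline to the Pre-dose visit.

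**What to change.** **SAP 6.1.8.** State that the early-termination value is used for Day 14 only when no Day 14 value exists. Keep the FAS analysis. Unless redacted text already does so, add the same Day 14 analysis without early-termination values, and report how many such values there are and their study days.

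**SAP Table 2.** Reconcile the 3-day and 3-business-day statements across SAP Table 1 and Protocol 6.1.3. Set the Baseline window to the agreed days, ending at Day -1. End Screening before that window begins, and align Day 7 with the schedule.

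**Cost.** One sentence, a few table limits, and one repeated Day 14 analysis per efficacy endpoint. No new data are needed, since the planned listings already hold the dates and dosing times. The added analysis leaves out discontinuers and is open to selection bias, so it should be labelled supportive and stand beside the FAS result, not replace it.

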## 4. Statistical Analysis and Reporting

### 4.1. Introduction

Data processing, tabulation of descriptive statistics, calculation of inferential statistics, and graphical representations will be performed primarily using SAS (release 9.4 or higher).

Commercially Confidential Information If the use of other software is warranted, the final statistical methodology report will detail what software was used for what purposes.

Continuous (quantitative) variable summaries will include the number of subjects (n) with non-missing values, mean, standard deviation (SD), median, minimum, and maximum.

Categorical (qualitative) variable summaries will include the frequency and percentage of subjects who are in the particular category for each possible value. In general, the denominator for the percentage calculation will be based upon the total number of subjects in the study population, unless otherwise specified. The denominator for by-visit displays will be the number of subjects in the relevant study population with non-missing data at each visit. If there is any missing value for a categorical analysis, a “Missing” category will be displayed as the last category in the table for the variable.

For weight, height, CCI one decimal place will be used for all summary statistics. For all other summaries, the minimum and maximum will be reported with the same degree of precision (i.e., the same number of decimal places) as the observed data. Measures of location (mean and median) and confidence interval boundaries will be reported to 1 degree of precision more than the observed data, up to 3 decimal places. Measures of spread (SD) will be reported to 2 degrees of precision more than the observed data, up to 3 decimal places.

Percentages will be presented to 1 decimal place, unless otherwise specified. Percentages equaling 0 or 100 will be displayed with no decimal places or percentage symbols.

Fractional numeric values will be presented with a zero to the left of the decimal point (for example, 0.12 – 0.30).

Unless otherwise indicated, all statistical tests will be conducted at the 0.05 significance level using 2-tailed tests, and *P* values will be reported. Corresponding 95% confidence intervals (CIs) will be presented for statistical tests, where applicable.

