#### 6.1.5. Handling of Dropouts or Missing Data

There was no replacement for subjects who had withdrawn from the study or were lost to follow up. Individual items of TETRAS-PS, CCI, and Kinesia scores will not be imputed as described in Section 6.1.8.

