#### **8.2.1. TETRAS Performance Subscale Scores**

The TETRAS-PS Subscale (Version 3.1) score includes the following 9 items: head tremor, face (including jaw) tremor, voice tremor, upper limb tremor (left/right), lower limb tremor, Archimedes spirals, handwriting, dot approximation task, and standing tremor. Scores for each item range from 0 to 4 in increments of 0.5. Derivation for the TETRAS-PS Total score is described in Section 6.1.8. For lower limb tremor, only the maximum of the item 5 scores will be used. The TETRAS-PS assessments will be administered by a certified rater (referred to as a local rater hereafter) at Screening, Pre-dose, Day 1, Day 7, Day 14, and Day 21. The TETRAS-PS assessments will also be recorded using videography for centralized evaluation and rating by independent blinded central raters (neurologists) with expertise in the assessment of ET. All scores (item scores and total scores) by both local and central raters will be analyzed in the same way as described below for central rater data.

Observed values and change from baseline in each item score and in TETRAS-PS total score by central rater will be summarized overall, by cohort (see Section 6.1.2), and by study visit using descriptive statistics.

Additionally, tests of hypotheses comparing mean and median TETRAS-PS total scores between baseline and subsequent study visits will be conducted using a 2-sided paired t-test or Wilcoxon signed rank test. The null hypothesis is that the change from baseline in TETRAS-PS total score to subsequent visit is 0 with a 2-sided alternative considering a difference not 0 (significant changes in tremor).

As a supportive analysis, change from Screening to Baseline and change from Day 14 to Day 21 in each item score and in TETRAS-PS total score will be summarized overall and by cohort (see Section 6.1.2) using descriptive statistics.

Commercially Confidential Information

Commercially Confidential Information

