Day 1, Post-dose						
n	XX	XX	XX	XX	XX	XX
Mean (SD)	XX.X (XX.XX)	XX.X (XX.XX)	XX.X (XX.XX)	XX.X (XX.XX)	XX.X (XX.XX)	XX.X (XX.XX)
Median	XX.X	XX.X	XX.X	XX.X	XX.X	XX.X
Min, Max	XX, XX	XX, XX	XX, XX	XX, XX	XX, XX	XX, XX
Change from Baseline						
n	XX	XX	XX	XX	XX	XX
Mean (SD)	XX.X (XX.XX)	XX.X (XX.XX)	XX.X (XX.XX)	XX.X (XX.XX)	XX.X (XX.XX)	XX.X (XX.XX)
Median	XX.X	XX.X	XX.X	XX.X	XX.X	XX.X
Min, Max	XX, XX	XX, XX	XX, XX	XX, XX	XX, XX	XX, XX

Abbreviations: CFB = change from baseline; ET = essential tremor; TETRAS-PS = Tremor Research Group Essential Tremor Rating Assessment Scale (TETRAS)-performance subscale (PS); SE = standard error.

Note: TETRAS-PS Total score is derived as the sum of all of the individual item scores, with the exception of item 5, only the maximum of the lower limb tremor scores will be counted. Each individual item question score ranges from 0 to 4, where higher scores indicate worse quality of life. A negative change indicates improvement.

[1] The baseline value is the last observation recorded prior to the first dose of treatment.

[2] Estimates for mean change from screening/baseline and accompanying 95% CIs and P values are from a paired t-test

[3] P-value for testing mean change from screening/baseline is based on a paired t-test with null hypothesis that the change in TETRAS-PS total score to subsequent visit is 0 with a 2-sided alternative considering a difference not equal to 0 (change in tremor).

[4] P-value for testing median change from screening/baseline is based on a Wilcoxon signed-rank test with null hypothesis that the change in TETRAS-PS total score to subsequent visit is 0 with a 2-sided alternative considering a difference not equal to 0 (change in tremor).

SOURCE: Listing 16.2.6.1.1

Table 14.2.1.1.1 (cont.)  
Summary of Central Rater TETRAS-PS Scores by Study Visit  
FAS and Per-Protocol Population

Parameter: TETRAS-PS Total Score

Study Visit Statistic	Full Analysis Set			Per-Protocol Population		
	Cohort-1 (N=XX)	Cohort-2 (N=XX)	Overall (N=XX)	Cohort-1 (N=XX)	Cohort-2 (N=XX)	Overall (N=XX)
Mean Change from Baseline (SE) [2] (95% CI for Mean Change from Baseline)	XX.X (X.XX) (XX.X, XX.X)					
P value for Mean Change from Baseline [3]	X.XXX	X.XXX	X.XXX	X.XXX	X.XXX	X.XXX
P value for Median Change from Baseline [4]	X.XXX	X.XXX	X.XXX	X.XXX	X.XXX	X.XXX
% Change from Baseline						
n	XX	XX	XX	XX	XX	XX
Mean (SD)	XX.X (XX.XX)					
Median	XX.X	XX.X	XX.X	XX.X	XX.X	XX.X
Min, Max	XX, XX					

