Note: TETRAS-PS Total score is derived as the sum of all of the individual item scores, with the exception of item 5, only the maximum of the lower limb tremor scores will be counted. Each individual item question score ranges from 0 to 4, where higher scores indicate worse quality of life. A negative change indicates improvement.

[1] The baseline value is the last observation recorded prior to the first dose of treatment.

[2] Estimates for mean change from screening/baseline and accompanying 95% CIs and P values are from a paired t-test

[3] P-value for testing mean change from screening/baseline is based on a paired t-test with null hypothesis that the change in TETRAS-PS total score to subsequent visit is 0 with a 2-sided alternative considering a difference not equal to 0 (change in tremor).

[4] P-value for testing median change from screening/baseline is based on a Wilcoxon signed-rank test with null hypothesis that the change in TETRAS-PS total score to subsequent visit is 0 with a 2-sided alternative considering a difference not equal to 0 (change in tremor).

SOURCE: Listing 16.2.6.1.1

**Programming Note:** Continue for all parameters. Parameters include: Head Tremor, Face (including jaw) Tremor, Voice Tremor, Upper Limb Tremor: Forward Outstretched Postural Tremor-Right, Upper Limb Tremor: Forward Outstretched Postural Tremor-Left, Upper Limb Tremor: Lateral Wing Beating Postural Tremor-Right, Upper Limb Tremor: Lateral Wing Beating Postural Tremor-Left, Upper Limb Tremor: Kinetic Tremor-Right, Upper Limb Tremor: Kinetic Tremor-Left, Lower Limb Tremor: Extended-Right, Lower Limb Tremor: Extended-Left, Lower Limb Tremor: Heel-Shin-Right, Lower Limb Tremor: Heel-Shin-Left, Archimedes Spirals-Right, Archimedes Spirals-Left, Handwriting, Dot Approximation Task-Right, Dot Approximation Task-Left, and Standing Tremor. Change from Screening should only be presented after the baseline visit.

Commercially Confidential Information

Commercially Confidential Information

Commercially Confidential Information

Commercially Confidential Information

Table 14.2.1.1.3  
Summary of Central Rater Categorical TETRAS-PS Item Scores by Study Visit  
FAS and Per-Protocol Population

Protocol Amendment: 1.0

Item Score	Full Analysis Set				Per-Protocol Population			
	Baseline [1] (N=XX)	Day 7 (N=XX)	Day 14 (N=XX)	Day 21 (N=XX)	Baseline [1] (N=XX)	Day 7 (N=XX)	Day 14 (N=XX)	Day 21 (N=XX)
Head Tremor								

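### Item-level mean percent change loses zero-baseline subjects who worsen, which shifts it toward improvement

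*SAP*

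**What the plan says.** SAP 6.1.8 gives the formula "Percent change from baseline = (change from baseline / baseline) \* 100" and then its only zero-baseline rule: "If both baseline and change from baseline are 0 then percent change from baseline will be set to 0". It does not mention a zero baseline followed by a positive score.

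Three other sections decide what happens to such a subject:

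- SAP 6.1.5, in a sentence that also covers the individual TETRAS-PS items, ends "Kinesia scores will not be imputed as described in Section 6.1.8".
- SAP 4.1 says "Continuous (quantitative) variable summaries will include the number of subjects (n) with non-missing values".
- SAP 8.2.1 says "Scores for each item range from 0 to 4 in increments of 0.5", and the table shells add "A negative change indicates improvement". Zero is therefore both a valid score and the best possible one.

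The shell for Table 14.2.1.1.1 (SAP 14.2) has an absolute "Change from Baseline" block at each visit, with a confidence interval and P values. Below it is a percentage version with n, mean (SD), median and range only. The programming note reads "Continue for all parameters. Parameters include: Head Tremor, Face (including jaw) Tremor, Voice Tremor" and goes on to list 19 item-level rows. The same shell serves the local-rater table (14.2.1.1.5) and the in-clinic sensor table (14.2.5.1).

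**The concern.** A subject at 0 on an item can only stay at 0 or get worse. The first outcome is kept as 0%; the second is undefined and goes missing. A subject who falls from a positive score to 0 counts as -100%. Whether a value is missing therefore depends on the direction of change, and the lost values are all unfavourable.

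The study has one arm and no control group in which the same artefact would show up. A reader could find a mean raw change of about zero printed above an apparent percentage improvement for the same item. SAP section 1 allows these outputs into study reports, submissions and manuscripts.

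**Working it through.** The plan states no percent-change figure to reproduce, so the check applies the 6.1.8 formula literally.

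**Rule as written.** For baseline b and follow-up f:
- b > 0: 100 x (f - b)/b
- b = 0 and f = 0: 0%
- b = 0 and f > 0: undefined, so missing

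**Worked example (assumed data, 30 subjects, no net change).** Eighteen subjects start at 0: 6 rise to 0.5 and 12 stay. Twelve start at 1.0: 6 fall to 0.5 and 6 stay.
- Mean raw change: (6 x 0.5 - 6 x 0.5)/30 = 0.00.
- SAP rule: the 6 who worsened are lost, so n = 24. Mean = (6 x -50%)/24 = -300/24 = **-12.5%**.
- All zero baselines excluded instead: -300/12 = -25.0% on n = 12. The 0-to-0 convention therefore halves the distortion here, and removing it would not be a repair.
- Ratio of means: mean baseline is 12 x 1.0/30 = 0.40, and 100 x 0.00/0.40 = **0%** on all 30.

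**No-effect simulation (assumed settings).** There were 400,000 subjects per setting. The underlying score is normal and limited to 0-4. Independent rating error is added at both visits, and scores are rounded to 0.5 and kept within 0-4. True mean change is zero.

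| Underlying mean / SD / error SD | Zero baselines | Mean % change, SAP rule |
|---|---|---|
| 0.5 / 0.5 / 0.3 | 31% | -7.0% |
| 0.3 / 0.4 / 0.3 | 43% | -13.9% |
| 0.2 / 0.5 / 0.35 | 48% | -15.3% |
| 1.0 / 0.6 / 0.3 | 13% | +2.05% |

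Mean raw change was about zero in every row. In the first row 12.2% of subjects are lost, which is 0.122 x 30 = 3.7 in a trial of 30. Excluding every zero baseline there gives -8.9%.

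**Wider grid (28 assumed no-effect settings).** In these, the underlying score was not itself limited to 0-4.
- In the 16 settings with 33-99% zero baselines the mean was negative, from -0.7% to -14.3%.
- In the 12 settings with 0-25% zeros it was positive, from +0.2% to +11.3%. Percent change is skewed upward at low non-zero baselines, and that outweighs the loss.
- In all 28 the SAP value lay below the value obtained by keeping the lost subjects with a denominator of 0.5. The loss itself always pushes toward improvement, even where the net mean is positive.

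**The case against.** The best case on the other side is that little rests on this row, and much of that stands.

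- The secondary endpoints are absolute changes in total and subscale scores and in sensor measures. Confidence intervals and P values attach to absolute change only. The text of 8.2.1 promises observed values and change for each item; item-level percent change comes in only because the shell is repeated.
- The loss can be seen. The percentage block prints its own n, mean raw change for the same item is in the same table, Table 14.2.1.1.3 counts every central-rater score level by visit, and all scores are listed. The median percent change was 0 in every simulated setting of the table above. However, a lower n does not say who was lost, and the score-level table gives separate counts by visit, not transitions.
- Sampling error is large. The SD of percent change in these simulations is 53 to 57 points, so with up to 30 subjects the standard error is about 10 to 11 (for example 57/√30 = 10.4). A shift of -7% is under one standard error. It is nonetheless systematic and would not average out with more subjects.
- The dropping out is inferred from the SAP's silence and its default handling; it is not written down.

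A reader might infer that the 0-to-0 convention creates the false improvement. The arithmetic shows the opposite. A reader might also carry the result over to the sensor tables, which share the shell. That was not tested, and a sensor baseline is the average of two readings, so an exact zero needs both to be 0.

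**Conclusion.** The gap is real and its direction is fixed. Followed literally, the formula removes only zero-baseline subjects who worsen, and this shifts the item-level mean percent change toward improvement. The fault lies in the subject-level ratio and the unhandled 0-to-positive case.

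The size is conditional. It rests on the share of zero baselines per item, which neither document gives, and on the assumed score and error distributions. Under those assumptions the no-effect mean runs from about +2% at 13% zeros to about -15% at 48%.

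It would be tempting to say that every item will show a false improvement, or that the efficacy conclusions are compromised. The documents support neither. With few zeros the net mean can be positive. The absolute-change tests and the primary safety endpoint do not use this quantity, and total and subscale scores would be touched only by a baseline total of 0, which is unlikely. Severity is minor.

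**What to change.** For individual TETRAS-PS items, central and local raters alike, replace the subject-level percent-change-from-baseline rows with 100 x (mean change)/(mean baseline) over all subjects with both values, or drop those rows and rely on absolute change. In either case, report by visit the number of zero-baseline subjects who worsened. State in 6.1.8 that subject-level percent change is used for total and subscale scores only. Treat a single sensor-task measure the same way only if zero baselines occur in it.

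Do not simply exclude all zero baselines: that gave -25.0% against -12.5% in the worked example.

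The cost is SAP wording and a change to the table shell, with no new data. The downside is that the item-level percentage loses its SD, median and range.
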